## 4. SUBJECT POPULATION

### 4.1. Number of Subjects

Ten patients will be enrolled in this study.

### 4.2. Inclusion Criteria

Subjects must meet all of the following inclusion criteria to be eligible for participation in this study.

1. Willing and able to provide written informed consent
2. Male or female, age  $\geq 18$  years
3. HCV RNA  $\geq 15$  IU/mL at Screening
4. All HCV genotypes (1 to 6)
5. Chronic HCV infection ( $\geq 6$  months) documented by prior medical history or liver biopsy
6. Classification as treatment naïve or treatment experienced:
  - a) *Treatment naïve* is defined as having never been exposed to approved or experimental HCV-specific direct-acting antiviral agents or prior treatment of HCV with interferon or ribavirin or DAAs (except for SOF-containing regimens).
  - b) *Treatment experienced* is defined as prior treatment failure or relapse to a regimen containing interferon either with or without RBV or DAAs that was completed at least 8 weeks prior to Baseline/Day 1.

The subject's medical records must include sufficient detail of prior virologic failure to allow for categorization of prior response (Reference Section 4.2), as either:

- a. Non-Responder: Subject did not achieve undetectable HCV RNA levels while on treatment, or
  - b. Relapse/Breakthrough: Subject achieved undetectable HCV RNA levels during treatment or within 4 weeks of the end of treatment but did not achieve SVR.
7. Cirrhosis determination (approximately 20% of subjects may have cirrhosis)
    - a. Cirrhosis is defined as any one of the following:
      - i) Any previous liver biopsy showing cirrhosis (e.g., Metavir score = 4 or Ishak score  $\geq 5$ )

- 
- ii) FibroMeter® score >0.442 or an AST:platelet ratio index (APRI) >2 during Screening
  - iii) Fibroscan with a result of >12.5 kPa at any time prior to or during screening.
- b. Absence of cirrhosis is defined as any one of the following:
- i) Liver biopsy within 2 years of Screening showing absence of cirrhosis
  - ii) FibroMeter® score <0.442 or APRI ≤ 1 performed during Screening
  - iii) Fibroscan with a result of ≤12.5 kPa within 6 months of Baseline/Day 1
- Fibroscan results will supersede FibroMeter® /APRI; liver biopsy results will supersede FibroMeter® /APRI or Fibroscan results and be considered definitive.
8. Liver imaging (ultrasound, CT scan or MRI) within 6 months of screening is required in patients with cirrhosis to exclude hepatocellular carcinoma (HCC)
9. Presence of mixed cryoglobulinemia (please see criteria on the note below).
10. Null or partial response to previous therapies for MC, including corticosteroids, cytotoxic agents (cyclophosphamide, azathioprine), hydroxychloroquine, methotrexate, mono- or combination therapy with IFN $\alpha$ /PEG-IFN and ribavirin, and/or CD20 depletion with Rituximab.
- a. Patients can be on ongoing treatment with one of the drugs described above at inclusion unless there is significant DDI.
11. Subjects has the following laboratory parameters at screening:
- a) ALT <10 x the upper limit of normal (ULN)
  - b) AST <10 x ULN
  - c) Adequate bone marrow function as indicated hematologic parameters listed below and/or bone marrow cellularity >60-70% average for age.
    - a. WBC >1500 /uL
    - b. Platelets > 50,000/uL
  - d) Direct bilirubin >2 x ULN
  - e) INR >1.5 x ULN unless subject has known hemophilia or is stable on an anticoagulant regimen affecting INR
12. Females of childbearing potential (as defined in Appendix 3) must have a negative serum pregnancy test at Screening and a negative urine pregnancy test on Baseline/Day 1 prior to treatment.

13. Male subjects and female subjects of childbearing potential who engage in heterosexual intercourse must agree to use protocol specified method(s) of contraception as described in Appendix 3.
14. Lactating females must agree to discontinue nursing before the study drug is administered.
15. Subject must be of generally good health, with the exception of chronic HCV infection, as determined by the Investigator.
16. Subject must be able to comply with the dosing instructions for study drug administration and able to complete the study schedule of assessments.

**Note: Definition of Mixed Cryoglobulinemia** (patients must meet one of the five overlapping syndromes listed below and the presence/documentation of cold-precipitable immune complexes in blood on two different occasions.

- Clinical evidence of cryoglobulinemia, overlapping syndromes:
  1. Cutaneous vasculitis (Raynaud's phenomenon, purpura, skin ulcers, livedo, acrocyanosis)
  2. Glomerulonephritis (hypertension, hematuria, nephrotic syndrome)
  3. Arthropathy (arthralgias, arthritis)
  4. Neuropathy (peripheral and/or central nervous system, distal sensorimotor, mononeuritis multiplex)
  5. Sicca syndrome (xerostomia, xerophthalmia)

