
question as to whether immunomodulating therapy plays a role at all in eradicating cryoglobulins long-term, and whether antiviral therapy alone is adequate. If the latter, appreciable morbidity and mortality may be saved in avoiding treating these potentially sick, often cirrhotic patients, with immunomodulatory therapies.

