## 2. OBJECTIVES

The **primary objectives** of this study are:

- To assess the efficacy of new direct acting oral antivirals: LDV/SOF FDC (Harvoni®) or SOF/VEL FDC (Epclusa®) in patients with chronic HCV infection and MC, measuring the proportion of subjects who attain SVR at 4 and 24 weeks after cessation of treatment.
- To assess efficacy of new direct acting oral antivirals: LDV/SOF FDC (Harvoni®) or SOF/VEL FDC (Epclusa®) in patients with MC secondary to chronic HCV infection:
  - A **complete response** is defined as disappearance of arthropathy or kidney involvement, and/or purpura, and >50% reduction in IgM-RF and cryocrit.
  - A **partial response** is a 10-50% reduction in cryocrit and one (but not all) clinical and laboratory signs of systemic vasculitis (see below) (33)

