### **3. STUDY DESIGN**

#### **3.1. Treatment plan and regimen**

This is a single-center, open-label study to evaluate the safety, tolerability and efficacy of new direct acting oral antivirals:

- Ledipasvir/Sofosbuvir 90mg/400 mg FDC (LDV/SOF;Harvoni®, for those subjects enrolled under protocol version 1 only) in patients with genotype 1 HCV infection and MC already enrolled in protocol version 1 or
- Sofosbuvir/Velpatasvir 400mg/100mg FDC (SOF/VEL; Epclusa®, for all subjects enrolled under protocol version 2) in patients with chronic genotypes 1-6 HCV infection and MC. All subjects enrolled in protocol version 2 will receive Epclusa® who have failed or only partially responded to other MC therapies.

Treatment duration is as follows:

Subjects that have been already enrolled and started treatment under protocol version 1 will continue and complete the planned treatment with LDV/SOF FDC (Harvoni®):

- Treatment naïve subjects will be treated for 12 weeks.
- Treatment experienced non-cirrhotic subjects will be treated for 12 weeks.
- Treatment experienced compensated cirrhotic subjects will be treated for 24 weeks.

Subjects enrolled under protocol version 2 will receive SOF/VEL FDC (Epclusa®):

- Treatment-naïve subjects will be treated for 12 weeks
- Treatment-experienced non-cirrhotic subjects will be treated for 12 weeks
- Treatment-experienced compensated cirrhotic subjects will be treated for 12 weeks

Approximately 20% of subjects may have cirrhosis.

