### **3.4. Cryoglobulinemia Response-Based Stopping Criteria**

The following on-treatment response-based treatment stopping criteria will be utilized:

- Unacceptable side effect of the drug (i.e. hypersensitivity reaction, abnormal liver function tests; gastrointestinal side effects).
- Paradoxical effect on the disease manifestations (i.e. increased of systemic vasculitis, renal failure).

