## **9. STATISTICAL CONSIDERATIONS**

This is a pilot study in which 10 patients will be enrolled to explore the efficacy of all-oral anti-viral therapy for symptomatic hepatitis C virus infection-related cryoglobulinemia.

With 10 patients in the study we will be able to estimate the rate of patients who obtain an SVR with a margin of error of approximately 15%.

We will use frequency table and 95% confidence interval to describe the rate of SVR in the total sample and the two subgroups of interest.

Results will be compared to previous published studies (28), as well as unpublished experience, that have delineated the natural history of type 2 cryoglobulinemia, and the response to immunomodulatory therapies, including IFN/Peg-IFN, Ribavirin and Rituximab (27).

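### The cryoglobulinemia response definitions and Section 9 give no rule for subjects whose cryoglobulinemia therapy is started or increased after Day 1

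*Combined protocol and SAP*

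**What the plan says.** **Entry.** Section 4.2, item 10, requires "Null or partial response to previous therapies for MC" and names corticosteroids, cyclophosphamide, azathioprine, hydroxychloroquine, methotrexate, interferon with or without ribavirin, and rituximab. Item 10a adds: "Patients can be on ongoing treatment with one of the drugs described above at inclusion unless there is significant DDI". It asks for no stable dose and says nothing about the period after Day 1.

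**Endpoint.** Section 2 makes MC response a primary objective. Complete response (CR) is "disappearance of arthropathy or kidney involvement, and/or purpura, and >50% reduction in IgM-RF and cryocrit". Partial response (PR) is a smaller fall in cryocrit together with one sign of vasculitis. Neither definition mentions concomitant MC therapy or names a visit. The synopsis repeats them unchanged.

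**Analysis.** Section 9 uses a frequency table and 95% confidence interval to "describe the rate of SVR in the total sample and the two subgroups of interest". It gives no CR/PR estimate. It does plan a comparison with earlier experience of the natural history of the disease "and the response to immunomodulatory therapies, including IFN/Peg-IFN, Ribavirin and Rituximab".

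**Purpose.** Section 1.2 says that the trial should help answer the "question as to whether immunomodulating therapy plays a role at all in eradicating cryoglobulins long-term, and whether antiviral therapy alone is adequate". Section 3.1 describes a single-center, open-label study, and there is no concurrent control.

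**The concern.** MC therapy added during the study is foreseeable from the protocol itself. Subjects have already had an inadequate response to MC therapy and may enter on it. Section 1.2 notes that MC can persist after viral clearance. Sections 3.4 and 7.2 stop study drug for worsening vasculitis or renal failure, and Section 3.6 keeps those subjects in follow-up to post-treatment Week 24.

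If immunosuppression is started or increased and the signs, IgM-RF and cryocrit then improve, the improvement may be due to the added drug. The definitions have no means of separating the two. Such a subject would sit on the antiviral side of a comparison with the same class of drug, in a trial asking whether the antiviral is enough alone. Without a preset rule, the choice of how to count that subject is made in an open-label study after the result is known.

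**Working it through.** **1. Is there a rule anywhere?**
- Section 2 and the synopsis (CR/PR): clinical signs, IgM-RF and cryocrit only.
- Section 4.2, item 10a: therapy at inclusion only.
- Section 5.4, Tables 1a and 1b: the prohibition rests on drug interactions, names none of the drugs listed in item 10, and ends with treatment.
- Section 3.5: lists stops under Section 3.4 as lack of efficacy, which is a reason for discontinuation. It assigns no CR/PR status and does not reach drugs added without stopping treatment or after treatment ends.
- Section 9: SVR only.

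No passage states how such a subject is classified. With no condition on therapy, meeting the thresholds is sufficient.

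**2. The plan's own precision figure.** Section 9 states a margin of about 15% for SVR with 10 patients and gives no expected rate. The Wald half-width, 1.96 × √(p(1−p)/10), equals 15% at p = 0.938; the exact half-width is 15.4% at 10/10. That figure does not depend on MC therapy and is not in dispute here. No figure is given for CR/PR.

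**3. Effect on the CR/PR rate.** Inputs: n = 10 (Section 4.1); X subjects meet the thresholds; k of those had added MC therapy. X and k are assumed, because the documents give neither.

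Rate regardless of added therapy = X/10. Rate without added therapy = (X − k)/10. The difference is k/10, so 10 points per subject, and the second rate can never exceed the first.

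Exact (Clopper-Pearson) limits for x responders: lower = 0.025 quantile of Beta(x, 11 − x); upper = 0.975 quantile of Beta(x + 1, 10 − x).

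| X | k | Rate | Exact 95% CI |
|---|---|---|---|
| 8 | 0 | 80% | 44.4 to 97.5 |
| 8 | 1 | 70% | 34.8 to 93.3 |
| 8 | 2 | 60% | 26.2 to 87.8 |
| 8 | 3 | 50% | 18.7 to 81.3 |

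From 8 to 7 responders the lower limit falls by 44.4 − 34.8 = 9.6 points.

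**4. How likely is at least one such subject?** The documents give no frequency. If each subject independently has probability q of added MC therapy, P(at least one of 10) = 1 − (1 − q)^10. For assumed q of 5%, 10%, 20% and 30% this is 40%, 65%, 89% and 97%. Not all of these subjects would also meet the thresholds.

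**5. Recording.** Section 5.4 requires concomitant drugs in source documents and eCRF to 30 days after the last dose. Section 6.3.2 assesses them at post-treatment Weeks 12 and 24. Week 24 is day 24 × 7 = 168, which is 168 − 30 = 138 days after the stated window closes. Section 8.3 requires drugs treating a serious adverse event to be recorded, and Section 10.5 asks for start and end dates and dose changes in the source notes.

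**The case against.** The strongest case on the other side is that this is a descriptive 10-patient pilot without a hypothesis test, that the documents nowhere say such a subject is a responder, and that a listing of MC drugs beside response would largely settle it. Item 10 also selects subjects in whom earlier MC therapy did not work well, and item 6b requires prior interferon-based HCV regimens to have been completed at least 8 weeks before Day 1.

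Part of this stands. Responder status is inferred from definitions that are silent on therapy. Item 10 makes it less likely that an unchanged background drug explains a response, and item 6b concerns treatment before entry. Neither deals with drugs added later. Counting response regardless of added therapy is also a legitimate choice, but it answers a different question from the one in Section 1.2. The small sample makes each classification weigh more.

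A reader might also infer three stronger things that the documents do not support:
- **That late MC drug data will be lost.** Sections 6.3.2 and 10.5 call for the information, and the Section 6 visit lists do not state eCRF entry for other assessments either. The Appendix 1 tables were not in the text available and could not be checked.
- **That the protocol treats a subject stopped for worsening vasculitis as a success.** Section 3.5 places such stops under lack of efficacy; the gap is that this is not carried into CR/PR.
- **That the true response rate is biased upward.** The number affected is unknown, and Section 1.2 notes that rituximab can itself provoke vasculitis at high cryocrits.

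**Conclusion.** The gap is real and should be closed before CR/PR is analysed. A primary objective has thresholds but no planned estimate, no time point and no rule for MC therapy started or increased after Day 1. Taken at face value, the thresholds give a confounded answer to whether antiviral therapy alone is adequate and to the comparison with immunomodulatory therapy.

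The size is 10 percentage points per reclassified subject, with the number of such subjects unknown. The conclusion assumes that the definitions are applied as worded and that no rule sits in the appendices; none of their listed titles concerns response. The difference between Sections 5.4 and 6.3.2 is a mismatch to reconcile. SVR is unaffected.

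**What to change.** 1. In Section 9, add CR and PR as n/10 with exact 95% CI at one named visit. Post-treatment Week 24 would fit: it is the later SVR time point in Section 2, and Section 6.3.2 schedules the full sicca and neurological testing there. Report two versions side by side:
   - *response without added MC therapy*, in which any immunomodulatory drug for MC started, or increased above its Day 1 level, before that visit counts as non-response. The rule should cover drugs beyond those named in item 10, whose list is not closed;
   - *response regardless of added MC therapy*.
2. List background and added MC therapy for each subject beside response, with drug, indication, dates and dose changes, including changes during screening.
3. Align Section 5.4 with Section 6.3.2 so that eCRF recording of MC drugs runs to post-treatment Week 24.

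The cost is a few paragraphs of analysis text and some extra eCRF entries at visits where concomitant drugs are already assessed. The headline rate may be lower. No clinical use of MC therapy is restricted. The change does not remove the attribution limits of an uncontrolled design or of background drugs continued unchanged.

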manifestations of disease. However, the use of first generation direct-acting antiviral agents (Telaprevir® and Boceprevir® linear NS3/4A protease inhibitors) was limited by frequent escape mutants, efficacy restricted to genotype-1, need to retain protocols including PegIFN and ribavirin, potential for significant drug interactions, and serious side effects. In a trial of combination therapy including Telaprevir® for 13 patients with MC, all had significant AEs, including asthenia (92%), anemia (84%), neutropenia and bacterial infection (54%) (10). Approval of an uridine nucleoside analogue that selectively inhibits HCV NS5B RNA-dependent RNA polymerase (Sofosbuvir) by the FDA late 2013 has led to proof-of-concept trials in which combination all-oral therapy has proven effective for both genotype 1 and other genotypes, with a number of other regimens under development. In particular, the combination of Sofosbuvir (SOF) and Ledipasvir (LDV) has been reported to have almost universal efficacy in a 12 week regimen for genotype 1, and the combination of SOF and Ribavirin (RBV) for genotypes 2-6 in a 24 week regimen (11,12). Most recently, the combination of Sofosbuvir and Velpatasvir (SOF/VEL), Epclusa®, has been shown to have pan-genotypic efficacy in pivotal studies (23,24) and is rapidly becoming standard-of care for chronic HCV infection (25). Inclusion of genotypes 1-6 in our study will allow us to correlate possible confounding factors (e.g. specific extra-hepatic disease manifestations, immunoglobulin V-region gene usage; IL28B genotype; HCV Core gene mutations) compared to the published experience for Sofosbuvir and Velpasvir for other genotypes (23,24). It will also allow us to increase enrollment from a diminishing pool of patients who have yet to undergo treatment with 12 week course of Epclusa® (sofosbuvir/velpatasvir) in compensated patients (Child-Pugh A). In addition, persistence of cryoglobulinemia even after viral clearance with the newer regimens has also raised the question of whether longer treatment regimens may be appropriate in the setting of significant extrahepatic disease (13). To date, only limited published experience exists with regard to the “post-viral” phase of HCV MC, consisting of retrospective analyses involving various genotypes and differing regimens of DAAs (19,26). Thus, the timing is right for a prospective trial of all-oral treatment with Epclusa® (SOF/VEL) to rigorously evaluate the effect on extrahepatic disease manifestations in patients with MC of all genotypes, and to re-establish the efficacy of antiviral therapy in halting the direct and indirect role of HCV in driving autoimmune disease and lymphoproliferation. Using an interferon-sparing regimen to treat patients with HCV-related cryoglobulinemia will help answer the

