- ACR20-70 score (for subjects with Rheumatoid arthritis). This score includes a physical exam, a HAQ and a blood sample to evaluate ESR or CRP.
- Assessment of cirrhosis. Presence or absence of cirrhosis will be assessed by Fibroscan or APRI score or FibroMeter®.
- Obtain blood samples for tests:
  - Hematology profile
  - Chemistry profile
  - Coagulation profile
  - HIV 1/2 antibody and Hepatitis B surface antigen. If patient has a negative serology performed in the last 6 months, it does not need to be repeated.
  - HCV antibody and HCV RNA
  - Determination of genotype and subtype of HCV infection
  - IL28B genotype. All patients will have genotype determined and screened for IL28B genotype CC in order to corroborate previous studies of patients with

MC with regard to both, and with regard to response to treatment (20). If patient has an historical IL28B, it does not need to be repeated.

- Analysis of cryoglobulinemia measuring cryoglobulins, analyzing cross reactive idiotypes, analysis of complement and HCV core ELISA.
- Serum  $\beta$ -hCG pregnancy test for females of childbearing potential only
- CRP and ESR
- Obtain urine sample for:
  - Urinalysis and urine creatinine
- Subjects meeting all of the inclusion criteria and none of the exclusion criteria will return to the clinic for the Baseline/Day 1 visit assessments.

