##### **6.4.1. Clinical Laboratory Analytes**

- Hematology profile: Hematocrit, Hemoglobin (Hb), Platelet count, Red blood cell count (RBC), White blood cell count (WBC) with differential (absolute and percentage) including Lymphocytes, Monocytes, Neutrophils, Eosinophils, Basophils, Reticulocyte count and MCV. These studies will be performed at Core Laboratory at Mount Sinai Hospital.
- Coagulation profile: INR, Prothrombin time (PT), Activated partial thromboplastin time (APTT). These studies will be performed at Core Laboratory at Mount Sinai Hospital.
- Chemistry profile: Alanine aminotransferase (ALT/SGPT), Aspartate aminotransferase (AST/SGOT), Albumin, Alkaline phosphatase, Creatine Kinase, Creatinine, Total Bilirubin (reflex to Direct Bilirubin), Glucose, Lipase, Potassium, Sodium; Fibrotest® /APRI calculation, and Direct Bilirubin at Screening only. These studies will be performed at Core Laboratory at Mount Sinai Hospital.
- Urinalysis: Appearance, Blood, Color, Glucose, Leukocyte esterase, pH, Protein, Urobilinogen. These studies will be performed at Core Laboratory at Mount Sinai Hospital.
- Urine creatinine level. This study will be performed at Core Laboratory at Mount Sinai Hospital.
- Virological Tests: Serologies for HCV, HBV and HIV. HCV RNA will be measured using the COBAS® TaqMan® HCV Test, v2.0 for use with Ampliprep. HCV genotype and subtype will be determined using the Siemens VERSANT® HCV Genotype INNO-LiPA 2.0 Assay. These studies will be performed at Core Laboratory at Mount Sinai Hospital.

- IL28B genotype will be determined by polymerase chain reaction (PCR) amplification of the SNP, rs12979860, with sequence specific forward and reverse primers and allele specific fluorescently labeled TaqMan® MGB probes. These studies will be performed at Core Laboratory at Mount Sinai Hospital.
- Pregnancy Tests: Serum  $\beta$ -hCG or Urine  $\beta$ -hCG.

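### Inclusion items 11d (direct bilirubin) and 11e (INR) are written as minimums in a list where every item is binding; 11e defeats its own exception, and 11d appears reversed in the same way

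*Combined protocol and SAP*

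**What the plan says.** Section 4.2 opens with a rule that binds the whole list: "Subjects must meet all of the following inclusion criteria to be eligible for participation in this study". Section 6.1.1 repeats it as the gate to Baseline/Day 1: "Subjects meeting all of the inclusion criteria and none of the exclusion criteria will return to the clinic".

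Item 11 of Section 4.2 lists laboratory values the subject must have at screening:

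- 11a and 11b: ALT and AST each below 10 x ULN.
- 11c: WBC above 1500/uL and platelets above 50,000/uL, under a heading about adequate bone marrow function.
- 11d: "Direct bilirubin >2 x ULN".
- 11e: "INR >1.5 x ULN unless subject has known hemophilia or is stable on an anticoagulant regimen affecting INR".

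Both 11d and 11e are checked at screening. Section 6.1.1 draws a coagulation profile, Section 6.4.1 places INR in that profile, and the chemistry profile in Section 6.4.1 ends with "and Direct Bilirubin at Screening only".

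On the population, Section 1.2 describes the SOF/VEL course as being for use "in compensated patients (Child-Pugh A"), and Section 3.1 provides for cirrhotic subjects only if compensated. Section 3.1 also says "Approximately 20% of subjects may have cirrhosis". Item 15 of Section 4.2 adds "Subject must be of generally good health, with the exception of chronic HCV infection", as the investigator judges.

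**The concern.** Read as printed, 11d and 11e require abnormal results. A patient with normal direct bilirubin cannot enter. Nor can a patient with normal INR who has neither hemophilia nor a stable anticoagulant regimen. Yet such patients fit the population described everywhere else in the protocol.

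There are two possible consequences, and the documents do not show which occurred. If the site applied the list literally, it turned away patients the study was meant to treat. If it applied the opposite direction, the notes that Section 10.5 requires as proof of eligibility will not match the approved criteria. With 10 planned subjects, each eligibility decision bears on one tenth of the sample.

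This point does not claim that decompensated patients would be enrolled, or that an endpoint definition or analysis method is affected.

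**Working it through.** The plan states no figure to reproduce here. The check is a reading of the two items under the rule that all must be met.

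**Item 11e: what the exception does under each direction**

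Exempt means known hemophilia or a stable anticoagulant regimen affecting INR.

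| Patient | As printed (minimum) | If it were a maximum |
|---|---|---|
| Not exempt, INR at or below 1.5 x ULN | Not eligible | Passes |
| Not exempt, INR above 1.5 x ULN | Passes | Not eligible |
| Exempt, INR at or below 1.5 x ULN | Passes only through the exception | Passes without it |
| Exempt, INR above 1.5 x ULN | Passes without it | Passes only through the exception |

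Under the printed sign, a patient whose INR an anticoagulant has raised above the limit already qualifies and needs no exception. The exception then helps only exempt patients whose INR is *not* raised, excusing them from a raised INR that everyone else must show. Under a maximum, it protects those whose INR is high for a known reason. The wording of the exception fits only the second case, so the sign and the exception work against each other. This follows from the sentence alone.

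**Item 11d: fit with the rest of the protocol**

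There is no exception clause, so the argument above does not carry over. Set against the other provisions:

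1. The list rule makes every subject with direct bilirubin at or below 2 x ULN ineligible, without exception.
2. The stated population is compensated (Sections 1.2 and 3.1) and in generally good health apart from HCV (item 15).
3. Expected mix: 10 x 0.20 = about 2 subjects with cirrhosis, and 10 - 2 = about 8 without. All 10 would still need direct bilirubin above twice the upper limit of normal.
4. The other liver tests in the item, 11a and 11b, are upper limits. The minimums in 11c are explained by their heading; nothing explains a minimum in 11d.

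No section states what bilirubin or INR these patients have. For 11d the result is therefore a mismatch of substance, not a contradiction between two sentences.

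**Is either limit corrected elsewhere?** Section 4.3 contains no bilirubin or INR limit. Its exclusion of Child-Pugh B or C covers only cirrhotic patients, comes without cut-offs, and applies whichever way 11d and 11e are read. It is context, not a correction. Nothing else in the available text restates either limit; the appendices are available only as a list of titles.

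**Extent of the literal exclusion.** Direct bilirubin: all values up to and including 2 x ULN. INR: all values up to and including 1.5 x ULN, outside the exception. Both ranges contain every value at or below 1 x ULN.

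**The case against.** Four points can be made on the other side.

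- *Item 11e can be parsed as a minimum.* It would release two groups from that minimum, and the exception would still do something for stable patients at or below 1.5 x ULN. The argument that an exempt patient already qualifies also applies only to those above the limit. This is correct as formal logic. What remains is that the rule so read defeats the evident purpose of the exception, and nothing in the protocol gives a reason to require a raised INR.
- *Item 11d is inferred.* It has no exception, no bilirubin values are given for the target population, item 15 rests on investigator judgment, and 11c shows that minimums do occur in this list. This stands as a limit on strength: 11d is less firmly established than 11e.
- *The sign may be an extraction error.* This cannot be ruled out without the original PDF. It is unlikely: the less-than signs in 11a and 11b and the less-than-or-equal signs in item 7b of the same section came through, and 11d and 11e both carry the same greater-than sign.
- *It is an obvious slip that the site would recognise, with modest consequences.* Perhaps so, but the documents do not show how the items were applied. These are binding entry criteria, and Section 10.2 requires IRB approval before a modification is implemented. Quietly applying the other direction does not repair the approved text.

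**Conclusion.** The concern holds: items 11d and 11e are wrong as written and must be fixed. For 11e, the conflict between sign and exception is visible in the sentence itself. For 11d, the reversal is a strong inference from its mismatch with the stated population, supported by the upper limits in 11a and 11b.

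The literal rule shuts out every patient with direct bilirubin in the normal range and every non-exempt patient with INR in the normal range. The number of the 10 subjects affected cannot be computed, because the documents give no bilirubin or INR distribution and no screening results. The conclusion assumes that the printed signs match the original PDF and that no unavailable page corrects them.

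**What to change.** First check the two signs against the original PDF. The sponsor-investigator should then reconcile 11d and 11e with the exception in 11e, with item 15 and with the population in Sections 1.2 and 3.1; confirm the intended direction and limit of each item; and submit the amendment to the IRB under Section 10.2. This review proposes no threshold.

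The eligibility source notes kept under Section 10.5 should be checked for how the two items were applied to subjects already screened, and any departures from the approved text recorded. The screening log in Section 10.4 holds codes, names and addresses, so it can identify who was screened but not which values were accepted.

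The cost is low: a two-line amendment and a check of one site's notes in a 10-patient study.
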